6.11 CMAP and Nerve Conduction Studies

Compound muscle action potential (CMAP) testing and nerve conduction studies will be conducted on the first two subjects during the index procedure and at or before the 30 day follow up. CMAP is a non-invasive test that causes minimal or no discomfort. A hand held electrical stimulator will be used to generate a bipolar electrical phrenic stimulation in the neck, while recording diaphragm electromyographic responses on the surface of the chest. These studies will be performed by an Electrophysiologist skilled in the performance of these tests who will make a clinical assessment regarding the effects of stimulation. The studies will measure the CMAP on both the left and right diaphragm as well as the conduction latency of the phrenic nerves before the initiation of treatment on the first two patients. This data will be compared to the measurement data generated at a follow up test performed post cessation of treatment. Electrical stimulation will only be performed on the left phrenic nerve (the smaller of the two lungs) on the first two patients, affording the opportunity to use the patient as their own control and assess any difference induced by the PEPNS therapy between the stimulation and unstimulating phrenic nerves and diaphragm of each patient using a comparison of the CMAP voltage amplitude and nerve conduction latency. Fluoroscopy may be done on first two patients if differences are seen in the CMAP and nerve conduction studies by the electrophysiologist for the treated phrenic nerve. The data will also be compared to the published literature for phrenic nerve conduction latency^{15,16} and CMAP^{17,18} voltage amplitudes.

6.12 Measurement of Diaphragm Thickness using Ultrasound

Diaphragm muscle thickness will be measured using a standardized technique described similar to that previously by Cohn et al¹⁹ and Ueki et al²⁰ and later modified by Francis et al.²¹ Imaging will be performed using the M-

Turbo ultrasound system (SonoSite, Inc) with a 7.5-10.0-mHz transducer probe or its equivalent in two-dimensional B-mode.

6.13 Electrocardiogram (ECG) and X-ray

The electrocardiogram testing will be conducted using 12 leads prior to the stimulation and during the stimulation approximately every 24 hours following standard hospital procedures for running this test so that a cardiologist can determine if there have been any ECG changes during or post stimulation.

A routine chest x-ray will be taken prior to the stimulation and at or before the 30 day follow up, to determine if there has been any obvious change in lung volume or degree of atelectasis (in comparison to the contralateral lung as a consequence of stimulation).

6.14 Secondary Performance Endpoint: Analyzing Phrenic Nerve Stimulation in Synchrony with MV Breaths

A breath by breath stim count analysis will be performed to determine the effectiveness of electrical stimulation on the inspiratory breaths stimulated. Effectiveness will be determined by measuring an effect on the work performed by the diaphragm and its ability to remain within normal physiological levels of work of breathing.

Figure 3. Sample Data Acquisition Data using Labchart for Qwye, Pwye, WOB and Stim Signals

The analysis will be performed for WOB as follows. A count will be performed to determine the number of stimulated breaths the measured WOB falls within a predetermined upper and lower control level for the stimulated breaths. This will be compared to the number of breaths electrically stimulated. These counts will be used to determine the effectiveness of electrical stimulation based upon percentage of electrical stimulation signals capturing breaths as intended.

6.15 Additional Study Data

Time to weaning from mechanical ventilation data will be collected and reported.

The effect of electrical stimulation on diaphragm thickness, blood gas parameters, vital signs, end tidal CO₂ and tidal volume may be characterized. To this end, stimulation will be stopped for a single period of 1 hour within the middle period of the 6 hour blood gas analysis collection period, when the patient has been deemed to be hemodynamically stable by the attending physician. Data will be collected on blood gasses, pulse rate, blood pressure, SpO₂, end tidal CO₂ and tidal volume at the end of the 1 hour period. This data will be used to characterize the effect of electrical stimulation on hemodynamics. The mode of ventilation will also be recorded because stimulation is predicted to have little effect on tidal volume in flow controlled modes whereas it is predicted to increase in pressure control modes of ventilation. Tidal volume may also be adjusted to be the same as when electrical stimulation was turned on to eliminate any confounding effects of decreased minute and tidal volumes when stimulation is turned off. All other parameters such as breath rate, PEEP, FIO₂ etc. will be kept the same.

The diaphragm thickness may be measured prior to the stimulation, at 24 hours and at 48 hours or after the completion of all of the stimulation using ultrasound when clinically feasible, i.e., 0 hours, 24 hours and 48 hours or end of stimulation.

7. PROCEDURAL GUIDELINES (Treatment Procedure)

7.1 Operator's Manual

Detailed instructions are provided for the console and lead insertion and all participating investigators will be trained on how to use the PEPNS System. Refer to LM0001 PEPNS System Operator's Manual for detailed information.

8. SITE SELECTION CRITERIA

Site Selection Criteria
Number of ICU beds & state of the art status of ICUs and staffing (minimum of 10 ICU beds)
Number of Ventilation Patients – enrollment capacity (minimum of 300 mechanically ventilated patients on an annual basis)

• Critical Care Research (previous & existing and no competing studies, etc.)• Outcomes (existing trials)• Dedicated ICU/Critical Care Research Nurse• Proficiency in mapping nerves with ultrasound and placing leads in the neck region within the ICU setting• None of the investigators can be in the FDA disqualification proceedings database.

9. SITES AND ENROLLMENT

Sites and Enrollment
Up to 2 trained and enrolling sites
Up to 10 patients at each site

10. PROCEDURE DURATION AND FOLLOW-UP

Procedure Duration and Follow-up
Up to 48 hours of continuous stimulation time
Upon expiration of the 48 hour stimulation period the stimulation will be turned off and the PEPNS multipolar leads will be removed from the patient.

Patient Follow-up
Each patient will be followed for a total of 30 days after stimulation end to determine if he/she experienced any adverse events with a clinic follow-up visit and for a chest x-ray. This follow up may occur within +7 days of the 30-day follow-up period giving an allowable follow-up range of 30 to 37 days for AE's and 30 ± 7 days for the chest x-ray.

The total expected duration of the clinical trial is up to 18 months once both sites start to enroll subjects.

11. STUDY SCREENING AND STUDY PROCEDURES

11.1 Screening

Potential study candidates undergo a screening evaluation that includes:

- An evaluation of their suitability for enrollment in the study by the site Investigator including their current state of health, demographics and medical history;
- Height, weight and body mass index (BMI)
- Neck diameter at the cricoid cartilage
- Ventilation information
- Blood pressure
- Chest x-ray

11.2 Index Procedure

Once the study subject or authorized representative signs an ICF and his/her eligibility to participate in the study is confirmed, the PEPNS System procedure can be initiated. A primary operator will be performing the PEPNS System procedure, but an additional qualified operator may be present or assisting. A Stimdia representative may also be present during index procedure to provide technical guidance to the primary operator.

The Investigator will follow the procedure technique outlined in LM0001, PEPNS System Operator's Manual.

Prior to the start of electrical stimulation, the subject's diaphragm thickness may be measured using ultrasound and the subject will have a 12 lead ECG. In addition, baseline standard blood gasses such as pH and paO_2 , paCO_2 , SaO_2 , HCO_3 etc. and exhaled gas analysis such as end-tidal CO_2 data will be garnered for up to 24 hours prior to stimulation.

A four pole pacing lead electrodes will be percutaneously placed beside the phrenic nerves using ultrasound guidance and the ultrasound screen shots will be captured if possible. The ease of gain pacing lead access and setup will be assessed and logged.

The subjects phrenic nerve(s) will then be electrically stimulated for up to 48 hours and device and procedure information, ventilation and PEPNS System stimulation will be recorded. In addition, patient vital signs including heart and respiratory rate, blood pressure, temperature, pH, paCO_2 , paO_2 , hematocrit, end-tidal CO_2 , will be collected when available unless otherwise specified in table 1 below. If the patient is weaned from the mechanical ventilator during this time the time to weaning will also be recorded. Also, a chest x-ray will be obtained if the patient has not had one in the last 30 days. In addition, Critical Care Pain Observation Tool^{22,23} (CPOT) and Richmond Agitation & Sedation Scale^{24,25} (RASS) assessments will be administered prior to the electrical stimulation and every 6 hours during it. Patients will also be physically observed for any muscle twitching during the simulation period to try and determine if any other nerves were stimulated. Diaphragm thickness may be measured again at 24 and 48 hours or at the end of the stimulation period.

The ability of the pacing lead to accommodate neck movement and patient positional changes will also be assessed and logged during electrical stimulation.

The ease of removing the pacing leads from the patient's neck will also be assessed during lead extraction and logged.

Compound muscle action potential (CMAP) testing and nerve conduction studies will be conducted on the first 2 subjects during the index procedure and at or before the 30 day follow up.

11.3 Follow-Up Visits

All subjects will be followed up at 30 days to 37 days for adverse events and 30 ± 7 days for the chest x-ray. At this time hospital discharge and ventilation weaning time data will also be collected. Table 1 summarizes all required and optional test and procedures throughout the study including each visit's compliance windows.

Table 1: Study Procedures and Follow Up

Test / Evaluation	Screening (within 2 days pre-procedure)	Index procedure	30 day follow up
Signed Informed Consent	X		
Subject Demographics	X		
Medical History	X		
Height/Weight/BMI	X		
Blood Pressure	X		
Chest x-ray	X ¹		X
12 lead ECG		X	
Lead Insertion assessment		X	
1 hr. cessation of electrical stimulation		X	
Patient movement / repositioning assessment		X	
CMAP ²		X	X
CPOT/RASS assessments		X	
Muscle twitching observation		X	
Ultrasound screen shots (optional) Ventilation settings and end-tidal CO ₂ required Stimulation Data Vital Signs / pulse oximetry Standard Blood gases: pH, paO ₂ , PaCO ₂ etc. Diaphragm thickness (optional)		X	
Lead Removal assessment		X	
Adverse Events		X	X
Device Malfunctions		X	

¹ It is acceptable if this has been taken up to 30 days prior to the screening visit.

² Only for the first 2 patients enrolled.

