6. STUDY DESIGN & METHODOLOGY

The study will examine performance and safety as defined in primary and secondary endpoints listed in Section 10. A maximum of up to 20 subjects will be enrolled in the study at up to 2 sites with up to 10 subjects per site. The final number of patients enrolled in the study will be based upon the time duration of the study and the rate of enrollment. In the first two patients, the investigator will stimulate the left phrenic nerve only and conduct CMAP tests and nerve conduction test on both phrenic nerves prior to and at least 3 weeks after the stimulation. These subjects will be examined 30 days' post study, to confirm safety of this method of stimulation of the phrenic nerve before enrolling the remaining patients up to a total of 20 subjects. After successfully demonstrating 30 day follow up on the initial two patients, stimulation will occur in both the left and right phrenic nerves simultaneously for the remainder of the trial. Typically, stimulation will occur once every 3 to 5 breaths and this decision will be left to the discretion of the attending physician. Figure 2 outlines the protocol for placement of the leads.

[figure not shown]

Figure 2. Study Left and Right Phrenic Nerve Pacing

Stimulation will occur for a maximum duration of 48 hours. A number of evaluations will also be conducted to measure the ease of placing and removing the stimulation leads as well as the ability of the lead to accommodate positional changes made by or to the patient.

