ECG (electrocardiogram) will be reviewed before during and after electrical stimulation to ensure electrical stimulation is not adversely affecting the heart. This will be evaluated by an expert in the reading of ECGs.

	PEPNS Study Statistical Analysis Plan	Document Number SAP0001	Rev. Level 1
CONFIDENTIAL: THIS DOCUMENT AND ALL INFORMATION CONTAINED HEREIN IS PROPRIETARY TO STIMDIA MEDICAL, INC. AND IS NOT TO BE DISCLOSED WITHOUT THE EXPRESS WRITTEN PERMISSION OF STIMDIA MEDICAL, INC.			

Table 3: Patient Vitals and PEPNS Data

Patient ID	Age (yrs)	Weight (kg)	Height (cm)	Body Mass Index (BMI)	IV Line (Y/N)	ET / Trach (E/T)	Neck circumference at the cricoid cartilage (cm)	Screening Blood Pressure	PEPNS System Lead Preparation	PEPNS System Lead Placement	PEPNS System Lead Securement	Lead Removal/ Skin Closure Assessment	Twitching?	Follow-up X-Ray Normal?	Adverse Events?	Device Malfunctions?
P03S01																
P04S01																
P05S02																
P06S02																
P07S02																
P08S01																
P09S02																
P10S02																
P11S01																
P12S02																
Mean																
Stdev																

ADDITIONAL EVALUATIONS

Briefly state the overall scientific objectives of the analyses, including the key unanswered questions that these analyses are designed to address. If necessary, provide additional detail to formulate the objectives in statistical terms. Include a brief summary of how each objective will be addressed in the analyses.

The clinical effect of electrical stimulation will also be examined for the following:

- Time to weaning from mechanical ventilation data.
- Diaphragm thickness at 0, 24 and 48 hours.

The period of time each patient was on ventilation before electrical stimulation and the time to wean will be reported. The number of attempts to wean the patient before and after electrical stimulation will also be reported, if available.

The trend in diaphragm thickness increase/decrease for each patient and the aggregation of patients will be evaluated over time. The trend in diaphragm thickness based upon its initial thickness will also be evaluated. Correlations in diaphragm thickness increase and neck circumference will also be reviewed.

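### From patient 3 on, the before/after chest x-ray comparison cannot reliably attribute a change in lung volume or atelectasis to stimulation

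*Protocol*

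**What the plan says.** **Purpose and timing.** Protocol 6.13 states: "A routine chest x-ray will be taken prior to the stimulation and at or before the 30 day follow up". The aim is to find any "obvious change in lung volume or degree of atelectasis (in comparison to the contralateral lung as a consequence of stimulation". This is a comparison over time and between sides, with a causal reading.

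**Baseline film.** Protocol Table 1 (section 11.3) puts the x-ray in the column "Screening (within 2 days pre-procedure", but its footnote adds: "It is acceptable if this has been taken up to 30 days prior to the screening visit". Protocol 11.2 words the rule differently: "a chest x-ray will be obtained if the patient has not had one in the last 30 days". That sentence does not mention screening, and it stands in the paragraph on the stimulation period. Exclusion 17 (elevated hemidiaphragm on x-ray) does not say which film counts.

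**Side stimulated.** Under Protocol section 6, the first two patients are stimulated on the left only. After their 30-day follow-up, "stimulation will occur in both the left and right phrenic nerves simultaneously for the remainder of the trial".

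**Follow-up film.** Protocol sections 10 and 11.3 allow 30 ± 7 days. Section 10 counts from the end of stimulation.

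**Analysis.** SAP Table 3, whose rows start at P03, has the column "Follow-up X-Ray Normal" with no side and no baseline x-ray column. The SAP paragraph on adverse events says the follow-up x-ray evaluation will be noted. SAP section 4 promises general summary tables of baseline and 30-day results.

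**The concern.** The protocol sets its own task: to show a change that followed from stimulation, using the other lung as comparator. Three other provisions each weaken that comparison in bilateral patients. The comparator is itself stimulated, the baseline film may come from before the acute episode, and the SAP has no variable that expresses a change.

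What is at stake is how the 30-day safety data can be read. CMAP is limited to the first two patients, and the optional diaphragm ultrasound ends at 48 hours or at the end of stimulation. For bilateral patients, the x-ray is therefore the only imaging or physiological test that Protocol Table 1 lists at 30 days; the rest is adverse-event collection. If the x-ray comparison is not interpretable, a first-in-human study loses what that film could add. A film that is not normal in an ICU survivor cannot be interpreted without a baseline, and a normal film does not say whether anything changed.

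**Working it through.** **1. The plan's own timing figure.** The Study Summary gives total participation of up to 41 days. The inputs are 2 days of screening (Table 1), 2 days of stimulation (48 hours, section 6) and follow-up to day 37 (section 10).

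- 2 + 2 + 37 = 41 days, which reproduces the figure.
- This works only if follow-up runs from the end of stimulation. Counted from the start of the index procedure, the sum is 2 + 37 = 39.

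**2. Age of the baseline film at the procedure.**

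- Table 1 footnote: 30 days before screening + 2 days of screening window = 32 days.
- Section 11.2, if its 30 days count from the procedure: 30 days.

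**3. Longest interval between the two films.** Interval = film age + stimulation + follow-up.

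| Baseline rule | Sum | Days |
|---|---|---|
| Table 1 footnote | 32 + 2 + 37 | 71 |
| Section 11.2, counted from the procedure | 30 + 2 + 37 | 69 |
| Film taken inside the 2-day screening window | 2 + 2 + 37 | 41 |

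**4. Can the film predate ventilation?** The documents set no limit on ventilation before the procedure, so prior ventilation time is an assumption here. With a 32-day-old film, the lead over the start of ventilation is 32 minus the days already ventilated:

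| Assumed prior ventilation (days) | Film may predate ventilation by up to (days) |
|---|---|
| 1 | 31 |
| 2 | 30 |
| 7 | 25 |
| 14 | 18 |

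No provision requires the film to follow intubation.

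**5. What the side comparison measures.** Let I be the change due to illness and recovery, assumed equal on both sides, and let S be the change due to stimulation.

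- Left-only patient: (I + S) − I = S. The contralateral comparison works.
- Bilateral patient: (I + S_left) − (I + S_right) = S_left − S_right, which is zero when the effect is symmetric.
- Bilateral patient, each side against its own baseline: I + S. A symmetric effect is now visible, but it is mixed with I. An older baseline film lets more of the acute illness into I.

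**6. How many patients have an unstimulated side.** By plan, 2 of up to 20 (10%), leaving 20 − 2 = 18 without one. If enrolment ended at P12, the last row of SAP Table 3, it is 2 of 12 (17%).

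**7. Whether the SAP can express the comparison.** Table 3 holds one follow-up reading, with no side and no baseline. The note on follow-up x-ray results and the general summaries in SAP section 4 do not define a paired change in lung volume or atelectasis.

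**The case against.** A reader might infer that the x-ray can show nothing about what happened after stimulation. The documents do not support that. A film is taken at 30 ± 7 days, a one-sided change stays visible, and the footnote permits an old baseline without requiring one. Section 11.1 lists a chest x-ray in the screening evaluation.

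A reader might also infer that the decision to enrol beyond patient 2 is undermined. That does not follow. The decision rests on left-only patients, in whom the contralateral comparison is valid and CMAP with nerve conduction on both sides is the direct test. SAP Table 3 starts at P03. Only the age of the baseline film could touch this step.

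Nor should the film be presented as the protocol's test for nerve injury. Section 6.13 names lung volume and atelectasis. The SAP links the x-ray to phrenic nerve damage only for the first two patients.

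Other objections have weight:

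- A normal/abnormal reading does not depend on the other side, so a bilaterally abnormal film would still be entered as not normal. That is true, but it is not a change from baseline.
- Table 3 is a listing shell, and the follow-up case report form is not shown and may hold more x-ray detail. The SAP still names no paired analysis of it.
- SAP section 5 foresees that some patients may be stimulated on one side only, so the counts above are as planned.
- The x-ray is not an endpoint and carries no hypothesis or power.
- A fresher baseline does not remove confounding. In a single-arm study, a film taken after intubation compared with one at day 30 still mixes stimulation with recovery, and recovery could mask harm.

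These limit the weight of the point. They do not restore the comparison in 6.13 for bilateral patients.

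**Conclusion.** The point holds for bilateral patients, planned as up to 18 of 20. There the contralateral lung is not an unstimulated comparator, and a symmetric change would show no side difference. The baseline film may be 32 days old at the procedure and the films 71 days apart (30 and 69 under the other reading of 11.2), so the film can predate the ventilation episode. By how much depends on an assumed prior ventilation time. The SAP defines no paired change.

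The conclusion is limited to attribution: a change in lung volume or atelectasis cannot reliably be put down to stimulation. It does not extend to the primary or secondary endpoints or to the comparator used in the first two patients. It assumes that patients from the third on are stimulated on both sides as planned.

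**What to change.** 1. **Protocol 6.13.** Limit the contralateral comparison to the two left-only patients. In bilateral patients, compare each side with its own pre-stimulation film.
2. **SAP Table 3.** Replace the normal/abnormal column with new or worse than baseline, left and right, and record the date of the baseline film.
3. **Baseline rule.** Reconcile Protocol 6.13, 11.2 and the Table 1 footnote on which film is the baseline. For this comparison, use the most recent film before lead insertion, preferably one taken after intubation. State which film exclusion 17 refers to.
4. **Reporting.** State that, with one arm, a change from baseline remains confounded by the acute illness and recovery.

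The cost is wording in both documents, one added field, and at most one chest x-ray in a patient without a recent film. Section 6.13 already plans a film before stimulation.

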11.4 Unscheduled Visit

In addition to scheduled follow-up visits, the participants will be instructed and encouraged to contact the Investigator at any time during the follow-up period if he/she has questions or concerns relating to the PEPNS System therapy. If the patient is seen by the Investigator between scheduled follow-up visits (i.e., not a study required visit):

- No adverse events noted during unscheduled visit – no forms need to be completed.
- Adverse event noted – The Adverse Event (AE) Case Report Form (CRF) needs to be completed for each event.

The patient will still be required to return for the next scheduled follow-up visit if the unscheduled visit is out of the compliance with the follow-up window.

If the patient is treated by a health-care professional other than the Investigator for treatment-related complications, the Investigator must request copies of the medical records and, if necessary, complete an AE CRF.

